#### **6.4.2 Missing Microbiological or Clinical Outcome**

For clinical and microbiological outcomes, subjects who are lost to follow-up or have missing or "indeterminate" outcomes will be included in the denominator as indeterminate for cure/eradication rate, i.e., considered as not responders. If judged by the investigator that a subject died due to pneumonia, BSI/sepsis or cUTI, the clinical outcome will be considered as clinical failure after the event of death. If a subject died due to other reasons, the clinical outcome will be considered as "indeterminate" after death.

For clinical outcome, if a subject received additional antibiotics for target disease (i.e., baseline infection) before the target date, the outcome will be considered as "clinical failure". If a subject did not receive additional antibiotics for target disease before the target date, the outcome will be considered as "indeterminate".

Missing values for other individual data points will remain as missing unless otherwise specified. All analysis will be based on observed case unless otherwise stated.

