#### **9.4 Handling of Missing Data**

Missing data will not be replaced. Details will be defined in SAP.

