## 9.4 Secondary Endpoints

The secondary endpoints of this study are the following:

- Clinical outcome per subject at EOT and FU (HABP/VABP/HCABP or BSI/sepsis)
- Clinical outcome per pathogen at EOT, TOC, and FU (HABP/VABP/HCABP, BSI/sepsis or cUTI)
- Clinical outcome per subject/pathogen at EOT, TOC, and FU (cUTI)
- Clinical outcome per subject/pathogen at EOT, TOC, and FU (HABP/VABP/HCABP + BSI/sepsis, overall)
- Clinical outcome per CR pathogen at EOT, TOC, and FU (HABP/VABP/HCABP, BSI/sepsis, cUTI, HABP/VABP/HCABP + BSI/sepsis, overall)
- Microbiological outcome (for baseline Gram-negative pathogens) per subject/pathogen at EOT, TOC, and FU (HABP/VABP/HCABP or BSI/sepsis)
- Microbiological outcome (for baseline Gram-negative pathogens) per subject at EOT and FU (cUTI)
- Microbiological outcome (for baseline Gram-negative pathogens) per pathogen at EOT, TOC, and FU (cUTI)
- Microbiological outcome (for baseline Gram-negative pathogens) per subject/pathogen at EOT, TOC, and FU (HABP/VABP/HCABP + BSI/sepsis, overall)

- Microbiological outcome (for baseline CR Gram-negative pathogens) per subject at EOT, TOC and FU (HABP/VABP/HCABP, BSI/sepsis, cUTI, HABP/VABP/HCABP + BSI/sepsis, overall)
- Microbiological outcome (for baseline CR Gram-negative pathogens) per pathogen at EOT, TOC, and FU (HABP/VABP/HCABP, BSI/sepsis, cUTI, HABP/VABP/HCABP + BSI/sepsis, overall)
- Microbiological outcome with documented carbapenem-resistant Gram-negative bacteremia (overall) at EOT, TOC, and FU
- Composite clinical and microbiological outcome at EOT, TOC, and FU (HABP/VABP/HCABP, BSI/sepsis, cUTI)
- All-cause mortality at Day 14 and Day 28
- Composite endpoint of survival and no change in antibiotic treatment due to either lack of therapeutic benefit or drug-related toxicity at TOC
- Survival time (HABP/VABP/HCABP, BSI/sepsis)
- CPIS parameters at EOT, TOC, and FU (HABP/VABP/HCABP only)
- SOFA score at EOT, TOC, and FU

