#### **9.4.1.7 Sequential Organ Failure Assessment Score**

Sequential Organ Failure Assessment score (SOFA) and its change from baseline will be summarized by treatment group per infection site at Baseline, EOT, TOC, and FU. Change from baseline will also be summarized. In addition, SOFA score regardless of primary infection diagnosis will be analyzed in a similar manner.

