#### **9.4.1.8 Clinical Pulmonary Infection Score**

For the HABP/VABP/HCABP subjects, CPIS at EOT, TOC, and FU will be summarized by treatment group.

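### SOFA and CPIS summaries at TOC and FU cover only patients alive and assessed, so if deaths differ by arm the means can mask harm or favour the arm with more deaths

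*SAP*

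**What the plan says.** SAP 9.4 lists both scores as secondary endpoints, SOFA as "SOFA score at EOT, TOC, and FU" and CPIS, for pneumonia patients only, at the same visits. SAP 9.4.1.7 says that the SOFA score and "its change from baseline will be summarized by treatment group per infection site at Baseline, EOT, TOC, and FU". SAP 9.4.1.8 says that "CPIS at EOT, TOC, and FU will be summarized by treatment group"; no change from baseline is planned for CPIS.

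Missing data are covered in SAP 6.4.2. After the rules for clinical and microbiological outcomes it says "Missing values for other individual data points will remain as missing unless otherwise specified" and then "All analysis will be based on observed case unless otherwise stated". Protocol 9.4 says "Missing data will not be replaced" and leaves the details to the SAP.

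Death is handled explicitly for the clinical outcome. If the infection caused the death, "the clinical outcome will be considered as clinical failure after the event of death"; any other death makes the outcome indeterminate, which counts as non-response. The supplementary clinical outcomes at EOT and TOC (SAP 9.2.2) count any death from Day 4 onward as failure. Neither rule reaches the SOFA and CPIS summaries.

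**The concern.** Deaths are to be expected here. Protocol 1.1 describes carbapenem-resistant infection as often fatal, and the exclusion criteria admit APACHE II scores up to 30. A patient who dies before TOC or FU leaves the SOFA and CPIS summaries at that visit, and nothing in SAP 9.4.1.7 or 9.4.1.8 tells the reader so.

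Once patients are selected on survival, the two arms are no longer the groups that were randomised. If the sickest patients die and more of them die in one arm, that arm's remaining patients are a more favourable selection. Their mean can then look as good as, or better than, the mean in the arm that kept more of its sick patients alive. At stake is how two descriptive secondary endpoints are read.

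**Working it through.** **The plan's own figure.** The only design figure is about 150 patients randomised 2:1, giving about 100 on cefiderocol: 150 × 2/3 = 100, leaving 150 × 1/3 = 50 on BAT. It reproduces. The documents give no expected mortality, SOFA mean or SD for this trial, so every input below is an assumption.

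**Which visits are affected.** TOC and FU are anchored at 7 and 14 days after the last infusion (SAP Table 6-1), so a patient who dies before the visit cannot have a score. EOT is the last treatment day, has no analysis window in SAP Table 6-1, and may be assessed within 24 hours of the last dose (Protocol Table 7-2). Some patients who later die can therefore have an EOT value.

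**Illustration for SOFA change.** Let the latent change have mean μ = −1 and the same SD in both arms. Let a proportion d die, with correlation ρ between death and latent change. The latent change is only a device, since no score exists after death. The survivor mean is

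μ − ρ × SD × φ(q)/(1 − d), where q is the standard normal quantile at 1 − d.

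- d = 0.15: q = 1.036, φ(q) = 0.2332, ratio 0.2332/0.85 = 0.2743.
- d = 0.30: q = 0.524, φ(q) = 0.3477, ratio 0.3477/0.70 = 0.4967.

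At SD 3 the apparent advantage of the higher-death arm is ρ × 3 × (0.4967 − 0.2743) = ρ × 0.667:

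| ρ | Survivor mean, 15% deaths | Survivor mean, 30% deaths | Higher-death arm looks better by |
|---|---|---|---|
| 0 | −1.00 | −1.00 | 0.00 |
| 0.3 | −1.25 | −1.45 | 0.20 |
| 0.5 | −1.41 | −1.75 | 0.33 |
| 1 | −1.82 | −2.49 | 0.67 |

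Over a wider range (SD 2 to 4, deaths 10–20% v 20–40%, ρ 0.5 to 1) the advantage runs from 0.15 to 1.18 points.

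**Check by simulation.** With 100 patients in the 30% arm and 50 in the 15% arm, SD 3 and 20,000 runs, the higher-death arm had the better observed mean in 51% of runs at ρ = 0, 73% at ρ = 0.5 and 86% at ρ = 0.8.

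**Counter-case.** Suppose one arm is truly worse by 0.5, 1 or 2 points, and death occurs in either arm above the same threshold, set to give 15% deaths in the better arm. Deaths in the worse arm become 19.2%, 24.1% and 35.6%. The observed differences are 0.31, 0.59 and 1.09. The harm is understated by roughly 40% to 45%, but the direction does not reverse.

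**Cell sizes.** SOFA is also summarised by infection site. On the planned mix in Protocol 3.2.1, BAT has about 50 × 0.50 = 25 pneumonia and 50 × 0.20 = 10 BSI/sepsis patients before restriction to the CR Micro-ITT population. One BSI/sepsis death removes about a tenth of that cell.

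**The case against.** The strongest reply is that these are descriptive tables beside a report that already shows the deaths. Much of that stands. Clinical cure requires a reduction in SOFA for pneumonia and BSI/sepsis, and in CPIS for pneumonia, and death counts as non-response in that outcome. All-cause mortality at Day 14, Day 28 and overall, Kaplan-Meier curves and a composite that includes survival are all planned. Summary statistics include the number of subjects (SAP 6.1), and the table shells are a separate document, so a footnote on deaths may already be intended.

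What remains is narrower. Days 14 and 28 count from the start of treatment and TOC and FU from its end, so the mortality tables do not give the deaths before each SOFA or CPIS visit. The number of subjects alone does not separate death from a missed assessment.

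A reader might infer more than the documents support:

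- **That the arm with more deaths will look better.** It need not: there is no bias at ρ = 0, and in the counter-case the difference shrinks without reversing.
- **That a large gap is hidden.** Scoring death at the SOFA maximum (6 × 4 = 24) would produce one, but it would mostly restate the assumed mortality difference in SOFA points.
- **That SOFA is formally tested.** SAP 6.2 names Section 9.4.1.7 as the exception to its no-testing rule. That section describes no test; the comparison described is the stratified one in 9.4.1.9. This looks like a wrong cross-reference and should be corrected.

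**Conclusion.** The concern holds as a minor reporting point. By the plan's own rule, SOFA and CPIS at TOC and FU describe patients alive and assessed, and the summaries are not labelled that way. Any distortion requires both a mortality difference between arms and a correlation between death and the score. Under the assumptions shown for SOFA (equal latent change, SD 3, deaths 30% v 15%) it is 0.00 to 0.67 points, and it could be larger or smaller under other inputs. No corresponding figure was worked out for CPIS, but the selection acts in the same way.

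The primary endpoint is unaffected: deaths are non-responses in the clinical outcome, and the cUTI endpoint is microbiological with missing results counted as non-response. Nothing here supports reading the plan as concealing mortality.

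**What to change.** In SAP 9.4.1.7 and 9.4.1.8:

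1. Label the observed-case summaries as among patients alive and assessed.
2. Show, by arm, the number who died before each visit.
3. Add one table per score by visit with death as the worst ordered category: died, worse than baseline, unchanged, improved. The last three follow the sign of the change from baseline. Show patients alive but not assessed separately.

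Dates of death are already collected (Protocol 7.8.1.1), and CPIS is recorded at screening, so its change from baseline can be derived. No numeric score for death has to be agreed. The cost is SAP wording and one extra descriptive table per score. The cross-reference in SAP 6.2 can be corrected in the same revision.

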#### **6.5 Baseline Definition**

- For microbiological endpoints, baseline pathogens are determined from appropriate clinical specimens collected within the 3 days prior to randomization in this study for subjects who have been treated previously with an empiric antibiotic regimen and failed treatment, both clinically and microbiologically (as defined in general inclusion number 4). For the other subjects, baseline pathogens are determined from appropriate specimens collected within the 48 hours prior to the start of the first infusion of study treatment. Clinical specimens obtained by the site within the 2 days prior to signing informed consent form could be acceptable as screening/baseline cultures for this study. If appropriate specimens are collected on multiple dates before the first infusion, the specimens collected on the latest date for each pathogen will be used to determine baseline pathogens.

If multiple specimens are collected within the above time range for baseline, the following rules will be applied:

- In case same Gram-negative pathogens with different quantification are obtained from multiple samples from the same specimen type (i.e., blood, urine, respiratory specimen, or infection site that caused septic shock) that qualified a patient eligible for this study, the pathogen with the highest quantification/classification is considered as the baseline pathogen. The priority of quantitation is listed below:
  1. Highest value in quantification
  2. Largest value in semiquantification
  3. Largest value in no-quantification
- In case same Gram-negative pathogens with same quantification are obtained from different specimens, the pathogen with the highest minimum inhibitory concentration (MIC) for 1. cefiderocol 2. Meropenem, 3. Imipenem, 4. colistin is considered as the baseline pathogen.

The appropriate clinical specimen type is sputum, tracheal aspirate, bronchoalveolar lavage (BAL) fluid, protected specimen brush, pleural fluid, lung biopsy for HABP/VABP/HCABP, blood for BSI/sepsis, or urine for cUTI. Tissue from primary infection site is also applicable for all baseline infection. Specimen that was collected from other site may be considered as appropriate specimen. This will be determined by the medical monitor.

Only for subjects with cUTI, the pathogen whose quantification is  $10^5$  colony-forming units (CFUs)/mL or more will be considered as baseline pathogen.

For the other efficacy and safety endpoints, baseline is defined as the last measurement obtained prior to receipt of the first infusion of study drug.

## **6.6 Study Day Definition**

Day 1 is the calendar day on which each subject takes initial investigational medicinal product (IMP). However, Day 1 is the calendar day of randomization for subjects who did not take any IMP. Previous day to Day 1 is expressed as Day -1, and days before Day -1 in Screening Period are expressed as Day -2, Day -3, ..., etc.

## **6.7 Handling for Microbiologic Data**

If a pathogen is identified from local laboratory data but it is not sent to central laboratory, the name reported by local laboratory will be used for analysis. In this case, MIC will be treated as unknown.

If a pathogen name is different between local and central laboratory, the name of the central laboratory will be used for the analysis. In that case, quantification will be considered as missing.

## **6.8 Additional Antibiotics**

Additional antibiotics are defined as systemic antibiotics with Gram-negative activity. The medical group will determine which medications have Gram-negative activity. If the route of administration is ophthalmic, transdermal, nasal, topical, or vaginal, the medication will not be considered as a systemic antibiotic. Concomitant medications ending before initial study treatment start date/time plus 3 hours will not be considered as additional antibiotics. Antibiotics for Gram-negative pathogens that are allowed to be received (see Clinical Study Protocol [Section 5.2.1.1](#)) from Day 1 or Day 2, they will not be considered as additional therapy, but if they are received on Day 3 or after, they will be considered as additional therapy.

Medical monitor will adjudicate additional antibiotics based on the available data if needed.

## **6.9 Study Drug Regimen at Day 1 and 2**

For efficacy analysis, response rate in the cefiderocol group will be calculated by cefiderocol monotherapy or not, and in the BAT group by colistin-based regimen or not.

Colistin-based regimen includes subjects who received “COLISTIN”, “POLYMYXIN” or “POLYMYXIN B” based on WHO Drug Dictionary Preferred Term (PT).

## 7. DEMOGRAPHIC AND OTHER BASELINE CHARACTERISTICS

### 7.1 Subject Disposition and Discontinuation

Subject disposition will be summarized for the all screened subjects. The following subjects' disposition categories will be included:

- Subjects who were screened
- Subjects who were screen failed

For the subjects who were screen failed, they will be also summarized by respective reasons.

Subject disposition will be summarized by treatment group for the all randomized subjects. The following subjects' disposition categories will be included:

- Subjects who were randomized
- Subjects who were randomized and treated
- Subjects who completed treatment
- Subjects who did not complete treatment
- Subjects who completed the study
- Subjects who discontinued early from the study

Subjects who received study drug for 7 days or more (for cUTI subjects, 5 days or more) will be considered as subjects who completed treatment. Subjects who did not complete treatment and subjects who discontinued early from the study will be also summarized by respective reasons.

The number of subjects in the ITT population, Micro-ITT population, CR Micro-ITT population, CR-ME population, and Safety population will be obtained by treatment group. The reasons for excluding subjects from each of the populations listed above will be summarized by treatment group.

### 7.2 Demographic and Baseline Characteristics

Demographic and baseline characteristics will be summarized with descriptive statistics for the CR Micro-ITT population, CR Micro-ITT 2 population, CR-ME population, Micro-ITT population, and Safety population. The distribution of demographic and other baseline characteristics shown in [Table 7-1](#) will be summarized by treatment group.

Summary statistics will be calculated for quantitative scale items, and frequency and proportion of subjects in each category will be obtained for qualitative (i.e., binary and nominal) scale items. Quantitative scale items except for height, body mass index, SOFA and CPIS will be categorized and tabulated by treatment group.

The baseline pathogen will be summarized for Micro-ITT and CR Micro-ITT. The baseline carbapenem-resistant pathogen will also be summarized. The pathogen which is collected from blood specimen at baseline will also be summarized.

The baseline pathogen will also be summarized for the MIC values and susceptibility defined by Clinical and Laboratory Standards Institute (CLSI) and European Committee on Antimicrobial Susceptibility Testing (EUCAST) of the baseline pathogen. For this analysis, MIC for cefiderocol, amikacin, aztreonam, ceftazidime-avibactam, imipenem, ceftolozane-tazobactam, ciprofloxacin, meropenem, cefepime, colistin, and tigecycline will be used and number of subjects, MIC 50, MIC 90, and range will be calculated for summary statistics of MIC. MIC 50 and 90 are defined as the smallest value no less than 50% and 90% of the data, respectively; MIC 50 and 90 will be calculated only when the number of subject with particular bacteria is 10 or more.

The reported medical history will be coded using Medical Dictionary for Regulatory Activities (MedDRA). Medical history will be summarized for the CR Micro-ITT population and Safety population for each treatment group by MedDRA System Organ Class (SOC) and PT.

**Table 7-1 Demographic and Baseline Characteristics**

Quantitative scale items	Age, height, weight, body mass index, creatinine clearance, total APACHE II score, baseline fever, SOFA score, CPIS
Binary or nominal scale items	Gender, race, ethnicity, region, infection site, clinical diagnosis, baseline fever group, medical history, prior therapy with Gram-negative coverage, number of Gram-negative pathogens from appropriate specimen, causal infection for BSI/sepsis, severity of the disease

APACHE II = Acute Physiology and Chronic Health Evaluation II; CPIS = clinical pulmonary infection score; SOFA = Sequential Organ Failure Assessment

Note: See Section 14 for categories.

## 8. STUDY CONDUCT

### 8.1 Protocol Deviations

For all randomized subjects, major protocol deviations will be listed. Major protocol deviations will be specified in the “Protocol deviation specification” separately. A final list of major protocol deviations will be determined based on data review prior to database lock.

### 8.2 Treatment Exposure and Compliance

Extent of treatment exposure is defined as the actual dosing period during which subjects took medication as follows:

(The day of the final IMP dose) – (The day of the first IMP dose) + 1 [day]

For the CR Micro-ITT population and Safety population, summary statistics of duration of treatment exposure will be calculated by treatment group based on EDC data. Also categorized duration of treatment will be summarized by treatment group (see Section 14 about category).

### **8.3 Study Drug Regimen**

Best available therapy and adjunctive antibiotics taken from randomization to the end of study will be coded using World Health Organization (WHO) Drug Dictionary (Sep 2015 or later). The number and percentage of subjects taking BAT or adjunctive medications will be summarized by Anatomical Therapeutic Class (ATC) and PT for each treatment group for the CR Micro-ITT population and Safety population. Although a subject may have taken 2 or more medications, the subject is counted only once within an ATC classification. The same subject may contribute to 2 or more PTs in the same classification. All study drug administration data will be listed by subjects.

In addition, study drug regimen for Gram-negative pathogen that is received at Day 1 and Day 2 after first study drug administration will be summarized by treatment group for CR MITT and safety population. Study drug regimen includes only cefiderocol or BAT/adjunctive therapy and does not include concomitant medications. Generic names will be used for this summary.

### **8.4 Prior Therapy and Concomitant Therapy Other Than Best Available Therapy/Adjunctive Antibiotics**

Prior and concomitant medications will be coded using the WHO Drug Dictionary. If a subject received cefiderocol as concomitant medication, this will be reported as cefiderocol. Prior medications are defined as medications that were taken prior to the first dose date/time of the study drug. Concomitant medications are defined as medications that were taken on or after the first dose date/time of the study drug.

The number and percentage of subjects taking concomitant medications or procedures will be summarized by ATC and PT for each treatment group for the CR Micro-ITT population and Safety population. Although a subject may have taken 2 or more medications, the subject is counted only once within an ATC classification. The same subject may contribute to 2 or more PTs in the same classification. Prior medications or procedures will be summarized in the same manner for the CR Micro-ITT population and Safety population.

## **9. EFFICACY**

The primary population for efficacy analyses will be the CR Micro-ITT population. CR-ME population will be used as a supplementary analysis for primary efficacy endpoint. Micro-ITT population will be used to check the consistency of results for primary efficacy endpoints. Also, unless stated otherwise, a confidence interval (CI) of proportion will be calculated using the Clopper-Pearson method.

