#### **4.4.2.3 cUTI Specific Exclusion Criteria**

Patients who meet any of the following criteria at Screening will be excluded from the study:

1. Patient's urine culture at study entry isolates more than 2 uropathogens, regardless of colony count, or patient has a confirmed fungal cUTI
2. Patients with asymptomatic bacteriuria, the presence of  $>10^5$  CFU/mL of a uropathogen and pyuria but without local or systemic symptoms [30]
3. Patients with an ileal loop for urine outflow (for patients with BSI/sepsis and an ileal loop are eligible)
4. Patients with acute uncomplicated pyelonephritis, ie, absence of anatomic urinary tract abnormality
5. Patients with vesico-ureteric reflux

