## 9.1 Efficacy Assessment

### 9.1.1 Clinical Outcomes for EOT and TOC

The clinical outcomes will be assessed by the investigator according to the following criteria established for each infection site at EOT and TOC. In case treatment duration is extended beyond 14 days, an additional clinical outcome will be assessed on Day 14. The clinical outcomes will be entered in the electronic case report form (eCRF).

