### **9.1.3 Microbiological Outcomes per Baseline Pathogen for EOT and TOC**

The microbiological outcomes per baseline pathogen will be determined by the sponsor according to the following criteria established for each infection site at EOT and TOC. In case treatment duration is extended beyond 14 days, an additional microbiological outcome will be assessed on Day 14.

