##### **9.4.1.1 Clinical Outcome**

For the clinical outcome per subject, the outcomes will be summarized and the cure rate and its 95% CI at EOT, TOC (only for cUTI) and FU will be calculated by treatment group per infection site (HABP/VABP/HCABP, cUTI, and BSI/sepsis). The clinical response rate will be calculated as the proportion of subjects whose clinical outcome is clinical cure at each point. In addition, the clinical outcome per subject for HABP/VABP/HCABP + BSI/sepsis and overall will be analyzed in a similar manner. For Micro-ITT, CR-MITT2 and CR-ME population, same analysis will be applied.

In addition, the outcomes will be summarized and the cure rate at TOC will be calculated by treatment group per study drug regimen and antibacterial treatment regimen at Day 1 and Day 2.

For the clinical outcome per pathogen, the outcomes will be summarized and the cure rate and its 95% CI at EOT, TOC and FU will be calculated by treatment group per infection site. In addition, the clinical outcome per subject for HABP/VABP/HCABP + BSI/sepsis and overall will be analyzed in a similar manner. Clinical outcome per CR pathogen will also be summarized. For the CR-MITT2 population, the same analysis will be applied.

In addition to the analyses described above, the clinical cure rate per pathogen at TOC will also be tabulated by the MIC values and susceptibility defined by CLSI of the

baseline pathogen. For this analysis, MIC for cefiderocol, amikacin, aztreonam, ceftazidime-avibactam, meropenem, ceftolozane-tazobactam, ciprofloxacin, imipenem, cefepime, colistin, and tigecycline. For European Medicines Agency (EMA), the same analysis will be performed with the susceptibility defined by EUCAST.

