#### **9.4.1.2 Microbiological Outcome**

For the microbiological outcome per subject, the outcomes will be summarized and the eradication rate with 95% CI by treatment group per infection site at EOT, TOC (only for HABP/VABP/HCABP and BSI/sepsis) and FU will be calculated. The eradication rate is the proportion of subjects whose all of baseline Gram-negative pathogen(s) are eradicated at each time point. In addition, the microbiological outcome per subject for HABP/VABP/HCABP + BSI/sepsis and overall will be analyzed in a similar manner. For Micro-ITT, CR-MITT2 and CR-ME population, same analysis will be applied.

In addition, the outcomes will be summarized and the cure rate at TOC will be calculated by treatment group per study drug regimen and antibacterial treatment regimen at Day 1 and Day 2.

For the microbiological outcome per subject with documented carbapenem-resistant Gram-negative bacteremia at baseline, the outcomes will be summarized and the eradication rate with 95% CI by treatment group at EOT, TOC and FU will be calculated as the proportion of subjects who have documented carbapenem-resistant Gram-negative bacteremia at baseline to subjects who experience eradication of baseline documented carbapenem-resistant Gram-negative bacteremia. For this analysis, the same criteria of 9.2.4.3 and 9.2.5.3 will be used but only considering blood sample.

For the microbiological outcome per pathogen, the outcomes will be summarized and the eradication rate with 95% CI will be calculated per infection site by treatment group at EOT, TOC and FU will be calculated. The microbiological outcome per pathogen only including baseline carbapenem-resistant pathogen will also be summarized. For the CR-MITT2 population, the same analysis will be applied.

In addition to the analyses described above, the eradication rate per pathogen at TOC will also be tabulated by the MIC values and susceptibility defined by EUCAST of the baseline pathogen. For this analysis, MIC for cefiderocol, amikacin, aztreonam, ceftazidime-avibactam, imipenem, ceftolozane-tazobactam, ciprofloxacin, meropenem, cefepime, colistin, and tigecycline.

For supplementary analysis, the eradication rate, defined in Section 9.3.2, per pathogen at TOC will also be tabulated by the MIC values and susceptibility defined by CLSI.

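### Per-pathogen rates pooled across species would get Clopper-Pearson intervals that count a patient with two pathogens twice; those intervals are too narrow, mainly for clinical outcome

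*SAP*

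**What the plan says.** The default in SAP section 9 is that "unless stated otherwise, a confidence interval (CI) of proportion will be calculated using the Clopper-Pearson method".

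Two secondary analyses take up that default without naming another method:

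- SAP 9.4.1.1: "For the clinical outcome per pathogen, the outcomes will be summarized and the cure rate and its 95% CI at EOT, TOC and FU", by treatment group and infection site.
- SAP 9.4.1.2, again split by arm: "For the microbiological outcome per pathogen, the outcomes will be summarized and the eradication rate with 95% CI will be calculated per infection site".

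The two outcomes are defined at different levels. Clinical outcome is one investigator judgement per subject and visit (SAP 9.1.1: "The clinical outcomes will be assessed by the investigator according to the following criteria established for each infection site at EOT and TOC"), and the SAP has no pathogen-level clinical definition. Microbiological outcome is judged pathogen by pathogen (SAP 9.1.3: "The microbiological outcomes per baseline pathogen will be determined by the sponsor according to the following criteria established for each infection site").

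The plan allows for patients with several pathogens. SAP Table 7-1 tabulates the "number of Gram-negative pathogens from appropriate specimen", and SAP Table 14-2 has a mixed category for the type of resistant baseline pathogen. For cUTI, Protocol 4.4.2.3 excludes a patient only if the "Patient's urine culture at study entry isolates more than 2 uropathogens, regardless of colony count", so two are permitted. Neither document mentions clustering within patient.

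**The concern.** Clopper-Pearson limits are exact for a binomial count of independent units. If the unit is a pathogen and the row covers an infection site, a patient with two species contributes two entries. For clinical outcome, the second entry is a copy of the first. The denominator grows without any new patient, and the interval shrinks.

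The trial does almost no testing (SAP 6.2), so intervals are its main statement of uncertainty and a 95% label should be accurate. At stake is the apparent precision of some secondary per-pathogen rates.

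**Working it through.** **Planned sizes.** SAP 4.3 gives about 150 subjects randomized 2:1. 150 × 2/3 = 100 on cefiderocol, which matches the plan's figure, and 150/3 = 50 on BAT. With the site mix in SAP 4.2 (about 50% pneumonia, cUTI at its 30% maximum, remaining 20% BSI/sepsis), the cells are 50 and 25, 30 and 15, and 20 and 10. CR Micro-ITT cells would be smaller.

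**Assumptions.** The documents do not give the share f of patients with two baseline pathogens, so f = 10% to 50% is used. True rates run from 0.30 to 0.80.

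**Design effect.** If a patient has m pathogens sharing one outcome, the design effect is Σm²/Σm. With one or two pathogens per patient:

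- Clinical outcome (within-patient correlation 1): (1 + 3f)/(1 + f). This is 1.18 at f = 10%, 1.33 at 20%, 1.46 at 30% and 1.57 at 40%.
- Eradication with correlation ρ: 1 + ρ × 2f/(1 + f). At f = 20% and ρ = 0.3 this is 1 + 0.3 × 0.4/1.2 = 1.10.

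**One example.** Take 50 cefiderocol pneumonia patients, f = 20% and an assumed cure rate of 60%. There are 40 + 2 × 10 = 60 pathogens, and the effective n is 60/1.33 = 45.

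| Basis | Count | 95% limits | Width |
|---|---|---|---|
| Pathogens, as planned | 36/60 | 0.465–0.724 | 0.259 |
| Patients | 30/50 | 0.452–0.736 | 0.284 |
| Effective n | 27/45 | 0.443–0.743 | 0.300 |

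The pathogen-based interval is 1 − 0.259/0.300 = 14% narrower than the adjusted one. It is also narrower than the per-patient interval, although no patient was added.

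**Coverage, pooled clinical outcome.** Mean coverage of the nominal 95% interval, by exact enumeration over the range of true rates:

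| Patients in cell | f = 0 | 10% | 20% | 30% | 40% |
|---|---|---|---|---|---|
| 50 | 96.7% | 94.8% | 93.2% | 91.5% | 90.6% |
| 25 | 97.0% | 95.7% | 93.9% | 91.8% | 91.3% |
| 10 | 97.9% | 96.5% | 95.4% | 93.8% | 92.5% |

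The f = 0 column shows why modest sharing does little harm: Clopper-Pearson is conservative and has coverage to spare.

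**Coverage, pooled eradication, 50 patients (simulated, correlation assumed).** With ρ = 0.3 and f = 20% to 30%, coverage is 93.8% to 96.4%. With ρ = 0.6 and f = 50%, it is 90.8% to 92.0%.

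**Check of the remedy.** Clopper-Pearson on the effective n, applied to pooled clinical outcome, stayed above 95% at every true rate enumerated, in all six planned cell sizes and for f up to 50%.

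**The case against.** The strongest objection is that the SAP never says species are pooled. Its per-pathogen text gives treatment group and infection site but not the row unit, and SAP section 1 leaves table layouts to a separate shells document. Parts of the SAP suit species rows. Section 7.2 counts subjects with a particular bacterium, and section 6.5 reduces repeat isolates within a patient: "the pathogen with the highest quantification/classification is considered as the baseline pathogen". In a species row each patient enters about once, the design effect is 1, and Clopper-Pearson is valid. This stands, and it limits the point to pooled rows.

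It does not remove the point. The wording by site and arm permits pooling, and SAP 9.4 lists per-pathogen outcomes for combined sites and overall. SAP 9.4.1.3 describes its per-pathogen clinical rate as a proportion of subjects, so the unit is unsettled within the SAP itself.

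Three further objections also stand. Sharing at about 10% leaves coverage near nominal. Eradication can differ within a patient, so its effect is weaker. The intervals are descriptive, with no test attached.

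A reader might infer that every per-pathogen interval is too narrow, or that the 95% level certainly fails. The documents support neither: pooling is not specified, and a table of pathogen counts shows that multi-pathogen patients can occur, not how often.

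**Conclusion.** The point holds for per-pathogen rows pooled across species, and mainly for clinical outcome. There the planned interval treats duplicate results as independent and is too narrow.

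The size depends on an unstated share of multi-pathogen patients. At an assumed 20% to 40%, mean coverage would be about 93% to 91% with 50 patients. It stays near 95% at about 10%, and in a cell of 10 patients at up to about 20%. The figures assume at most two pathogens per patient and planned cell sizes. No cap is stated outside cUTI, so three or more pathogens in a patient would enlarge the effect.

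Single-species rows are sound. The primary analysis and all per-subject intervals are untouched, so no main conclusion of the trial depends on this. It is a minor improvement to the SAP.

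**What to change.** In SAP 9.4.1.1 and 9.4.1.2:

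1. State the unit and denominator of each per-pathogen rate, and whether rows are by species or pooled.
2. Keep Clopper-Pearson for single-species rows in which each patient counts once.
3. In any row pooled across species, either omit the interval, as the supplementary per-pathogen rates in SAP 9.4.1.3 and 9.4.1.4 already do, or compute Clopper-Pearson on the effective n, (Σm)²/Σm², with the observed rate times that n as the count. For eradication this is conservative, because it assumes a within-patient correlation of 1.

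Do not use a patient-level percentile bootstrap in these cells. In simulation with 20% sharing, its coverage was around 90% with 10 patients, below the unadjusted interval's 95.4%. It also collapses to zero width when all outcomes agree.

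The cost is a few sentences of SAP text, minor programming and slightly wider secondary intervals. No data collection changes.
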